7.7.3 Antibody Test

Antibody testing results will be presented in a data listing. The listings for subjects with at least one positive neutralising (baseline or post baseline) will be provided separately.

The number and percentage of subjects with the presence of neutralising BTX-A antibodies at study baseline, and post-baseline visits will be presented in the shift tables. The number of neutralising BTX-A antibodies seroconverters (subjects having a negative result at study baseline and at least one positive result at one post-treatment time point) and the time by when the subjects seroconverted will be reported.

7.7.4 Vital Signs

The normal ranges for the vital signs are displayed in Table 2 below:

Table 2 Vital Signs Normal Ranges

Parameter	Low	Normal	High
Diastolic Blood Pressure (mmHg)	<40	40-110	>110
Systolic Blood Pressure (mmHg)	<60	60-190	>190
Heart Rate (bpm)	<50	50-130	>130
Height (cm)	<120	120-200	>200
Weight (kg)	<35	35-120	>120

Vital signs data will be presented in a listing by treatment group and subject. Any unscheduled vital signs assessment will be presented in the listings. Vital signs include blood pressure (systolic/diastolic), heart rate, respiratory rate and temperature.

Summary statistics will be presented for actual values and changes from study baseline at each scheduled assessment by treatment group.

The number and percentage of subjects with abnormal values (Low and High) will be presented by treatment group.

For the DBPC period and each Dysport Cycle, shift from study baseline tables of the number and percentage of subjects with low, normal or high values will be presented.

7.7.5 Electrocardiograms

Not applicable.

7.7.6 Other Safety Variables

Pregnancy test, urinary tract ultrasound and physical examination data will be presented in data listings.

7.8 Primary Analysis of the Study

CCI [REDACTED]
[REDACTED]
[REDACTED]
[REDACTED]

[REDACTED]. The analysis will consist of all tables, figures and listings for the study described in this statistical analysis plan using all available data up to the cut-off date and a clinical study report will be written. A final analysis will occur when all subjects have completed the study (or at other timepoints if required to support regulatory agency submissions).

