15.2 Clinical Study Report

In order to support regulatory submission an ICH E3-compliant clinical study report (CSR) may be prepared prior to completion of the study. See [Section 9.6](#) for details regarding this primary analysis.

A final CSR will be prepared according to the ICH guideline on structure and contents of CSRs. A final CSR will be prepared where any subject has signed informed consent, regardless of whether the study is completed or prematurely terminated. Where appropriate an abbreviated report may be prepared. The CSR will be in compliance with any applicable regulatory requirements, national laws in force and will be in English.

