A patient may only be retreated if eligible based on the study retreatment criteria. The bladder diary device/portal may provide an indication that the patient is within 30% of their Baseline (Screening) UI level, however to confirm eligibility a manual calculation can be performed by multiplying the weekly number of UI episodes on the screening bladder diary by 0.7. If the subject has a current number of weekly UI episodes greater than this calculated number then the subject is within 30% of their Baseline UI level and meets the retreatment criterion #3.

Example calculation:

- Study Baseline (Screening) number of weekly UI episodes = 28 episodes
28 episodes x 0.7 = 19.6 (rounded up to 20)
- Subject is therefore eligible for retreatment if current weekly UI episodes are 20 or more.

Retreatment should ideally occur within 14 days of confirmation of eligibility for retreatment and can occur up to and including Week 104 following the first IMP administration of the first period.

Retreatment follow-up

Follow-up after each retreatment follows the same schedule as the first IMP administration (Treatment 1).

- Week 1 (Day 8) (telephone)
- Week 2 (Day 15) (clinic visit)
- Week 4 (Day 29) (telephone)
- Week 6 (Day 43) (clinic visit)
- Week 12 (Day 85) (clinic visit; the retreatment could be requested by subject from this visit)
- Every 12 weeks (telephone visits; until retreatment received or EOS at Weeks 104 to 116).

Details of the procedures performed at each Retreatment Follow-up Visit in the Dysport cycle are contained in [Appendix V](#).

End of Study Visit

The EOS Visit will take place between 104 and 116 weeks after the first IMP administration on Day 1. Subjects may receive study retreatment up to and including Week 104 and a minimum of 12 weeks of follow-up is required after each IMP administration. For those subjects completing the study, the EOS Visit will occur:

- At Week 104 after the first IMP administration, if it has been more than 12 weeks since the previous IMP administration.
- At Week 12 Retreatment Follow-up Visit, if the subject received their most recent IMP administration between Week 92 and Week 104 following their first IMP administration.

Early discontinuation

A subject who discontinues the study early should, if at all possible, be followed-up for at least 12 weeks following their most recent IMP administration and should attend the EOS Visit.

Duration of subject participation

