5.3 Safety Population

All subjects who received at least one IMP administration (including only partial administration) of the IMP. Safety subjects will be analysed according to their actual treatment received.

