Descriptive summary statistics for categorical variables will include frequency counts and percentages [n (%)]. The denominator for percentage calculations will be the number of subjects in the analysis population for the designated treatment cycles. Unless stated otherwise in the table shells (e.g. for the TEAE of MS relapse, the denominator only relates to the number of MS subjects),

Dates will be displayed as DDMMYYYY.

Overall, in the statistical tables the category “Missing” will be presented if the number missing is > zero for at least one treatment group.

Unless otherwise specified, the eCRF recorded strata (i.e. the correct strata) will be analysed for all used in all the data displays.

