- any UTI TEAEs
 - UTI TEAEs leading to withdrawal
 - serious UTI TEAEs
- TEAE leading to death

In view of the anticipated difference in duration of the Dysport and placebo treatment cycles, this overview table will also be provided including only TEAEs occurring any time after first dose of IMP until up to 12 weeks after first IMP treatment administration.

A similar overview table will be produced for the number and percentage of subjects with at least one of the following events occurred pre-treatment for randomised subjects. The number of occurrences of the following events will be presented as well.

- any AE
 - Intensity of AE (mild, moderate, severe)
- any SAE
 - any SAEs leading to withdrawal
- AE leading to death

TEAEs will be summarised overall, for DPBC cycle, and Dysport Cycles with the number and percentage of subjects with TEAEs presented by primary SOC and PT. In addition, this table will be provided including only TEAEs occurring up to 12 weeks after first IMP treatment administration. This will also be summarised by aetiology of NDO.

The same summaries for overall, for DBPC Cycle, and Dysport Cycles with the number and percentage of subjects with TEAEs presented by primary SOC and PT will be presented for serious TEAEs, IMP-related TEAEs, TEAEs leading to withdrawal, TEAEs of special interest, and other protocol defined TEAEs. TEAEs with PTs observed in $\geq 1\%$, $\geq 2\%$, and $\geq 5\%$ of subjects and IMP-related TEAEs with PTs observed in $\geq 1\%$, $\geq 2\%$, and $\geq 5\%$ of subjects will be summarised as well.

Additionally, TEAEs will be tabulated by decreasing overall PT frequency and intensity in each SOC and PT category.

The above will also be presented for SAEs.

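### Crude adverse-event percentages by Dysport Cycle are understated in a report written at a mid-study cut-off, because cycles still open at that date are counted in full

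*SAP*

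**What the plan says.** **When the tables are run.** Protocol 15.2 allows an early report: "In order to support regulatory submission an ICH E3-compliant clinical study report (CSR) may be prepared prior to completion of the study". SAP 7.8 says that analysis covers all planned tables, figures and listings, "using all available data up to the cut-off date and a clinical study report will be written". It is not the last analysis: "A final analysis will occur when all subjects have completed the study". Subjects are therefore still in mid-cycle at the cut-off. The text that sets the trigger is blacked out in SAP 7.8 and Protocol 9.6.

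**What is divided by what.** SAP 7.1: "The denominator for percentage calculations will be the number of subjects in the analysis population for the designated treatment cycles", unless a table shell says otherwise. The Safety Population (SAP 5.3) asks only for an injection: "All subjects who received at least one IMP administration (including only partial administration) of the IMP". SAP 7.7.1 gives the statistic: "TEAEs will be summarised overall, for DPBC cycle, and Dysport Cycles with the number and percentage of subjects with TEAEs". The same form is used for serious TEAEs, AESIs and the other protocol-defined TEAEs, which are UTIs. An event belongs to a cycle if it starts or worsens between that injection and the next one.

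**Follow-up.** SAP 2.2 states that "a minimum of 12 weeks of follow-up is required after each IMP administration". That holds for subjects who complete the study, not on an arbitrary calendar date.

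**Existing protection.** SAP 7.7.1 adds overview and SOC/PT tables limited to 12 weeks after the first IMP administration, because placebo and Dysport cycles are expected to differ in length. SAP 7.5 gives exposure in weeks across the study. By cycle it gives only counts of subjects.

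**The concern.** A subject retreated the day before the cut-off adds one to the cycle's denominator and has had one day in which to have an event. A subject injected 20 weeks earlier and not yet retreated has also been seen for only part of the cycle. For a given set of subjects, ending observation early can only lower a crude percentage of subjects with an event, so the direction of the error is known.

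The early report may support a submission, and SAP 7.1 makes safety over repeated treatment one of its two analysis aims. The tables that describe it would be low by an unknown amount. No table of time at risk by cycle is planned from which a reader could correct them.

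**Working it through.** The documents state no TEAE rate, cut-off date or number of subjects per cycle, so there is no figure of theirs to reproduce. All sizes below rest on assumptions.

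**Inputs from the documents**
- Randomised: 330, of whom 110 start on placebo (SAP 2.2).
- Injections more than 12 weeks apart, the last at Week 104 at the latest; exit at Week 104, or 12 weeks after a late injection (SAP 2.2).

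**Assumed inputs**
- Uniform accrual over 136 weeks. The planned period, first quarter 2016 to last quarter 2020 (Protocol synopsis), is about 4.75 × 52.2 = 248 weeks. Less 104 to 116 weeks of participation, this leaves 132 to 144.
- Retreatment interval of 12 weeks plus a lognormal time: median 36 weeks in total after Dysport (log-SD 0.8), 20 after placebo (log-SD 1.0).
- Constant hazard giving 20% risk at 12 weeks: λ = −ln(0.8)/12 = 0.0186 per week.
- Cut-off 12 or 26 weeks after the last randomisation.

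**Step 1: share of each cycle injected under 12 weeks before the cut-off (f).** Simulation gives:

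| Cut-off | Cycle 1 | Cycle 2 | Cycle 3 | Cycle 4 |
|---|---|---|---|---|
| +12 weeks | 3% | 12% | 16% | 20% |
| +26 weeks | 2% | 10% | 14% | 16% |

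At +52 weeks, Cycles 2 and 3 still have 4% and 10%.

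**Step 2: bias within a fixed 12-week window.** Let the recent injections be spread evenly over the last 12 weeks. The reported percentage is p × [(1 − f) + f × r], where r is the average fraction of the 12-week risk seen so far.
- Constant hazard: 12λ = 0.2231. The mean risk seen is 1 − 0.2/0.2231 = 0.1037, so r = 0.1037/0.2 = 0.519 and the table shows 20% × (1 − 0.481f).
- At +12 weeks: f = 3% gives 19.7%; 12% gives 18.8%; 16% gives 18.5%; 20% gives 18.1%. The shortfall is 0.3 to 1.9 points. Direct simulation gives 19.7, 18.9, 18.5 and about 18.0 to 18.1.
- Early onset (exponential, median 2 weeks): 12 × ln(2)/2 = 4.159 and e^(−4.159) = 1/64. The mean is 1 − (63/64)/4.159 = 0.763, so r = 0.763/(63/64) = 0.775. At f = 20% the table shows 20% × (1 − 0.225 × 0.20) = 19.1%, which is 0.9 points low.

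**Step 3: whole-cycle percentages, as SAP 7.7.1 would tabulate them.** The same subjects, observed to the cut-off or to the end of their cycle (shortfalls from unrounded values):

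| | Cycle 1 | Cycle 2 | Cycle 3 | Cycle 4 |
|---|---|---|---|---|
| Seen at +12 weeks | 46% | 40% | 33% | 24% |
| Cycle complete | 51% | 48% | 39% | 29% |
| Shortfall at +12, points | 5.3 | 8.0 | 6.6 | 4.3 |
| Shortfall at +26, points | 3.1 | 6.8 | 5.5 | 3.4 |

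In Cycle 2 at +12 weeks, 3.8 of the 8.0 points come from subjects already followed for 12 weeks or more whose cycle is still open.

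**Step 4: other assumptions.** With accrual over 130 weeks, a mean interval of 30 or 42 weeks and a true 12-week risk of 40%, the shares at +12 weeks are about 3%, 11–12%, 15–17% and 19–21%. Under constant hazard the 12-week percentage falls from 39.4–39.6% in Cycle 1 to 36.5–37.1% in Cycle 4.

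**The case against.** **Unseen text.** The opening of SAP 7.8 is redacted, and the denominator rule yields to table shells kept in a separate document. Either could hold a follow-up condition. That cannot be excluded, although using all available data points away from one.

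**Early events.** Protocol 8.1.2.11 says symptoms of toxin spread have been reported hours to weeks after injection. If most events come early, the 12-week bias is under 1 point in Cycles 1 to 4. This stands, and it limits the concern most for AESIs.

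**Partial cover.** Safety analysis is descriptive, a final analysis follows, and the 12-week tables cover Cycle 1 for the 220 subjects planned to start on Dysport. SAP 7.6.6.4 also gives Kaplan-Meier times between treatments by cycle. None of this supplies time at risk for events in the retreatment cycles.

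**Stronger readings that the material does not support.** A reader might infer that the cut-off is what makes repeat dosing look safer, with a bias that grows at every cycle. In Step 3 the fall from Cycle 1 to Cycle 4 is 22 points at the cut-off (46 to 24) and 22 points with complete cycles (51 to 29). The whole-cycle shortfall peaks in Cycle 2. The fall comes from later cycles being shorter under the Week 104 limit, and it would persist in the final report. Only the 12-week bias tends to grow with cycle number. Nor do recent injections simply count as event-free: any event before the cut-off is counted.

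**Conclusion.** The concern holds. Followed as written, the visible text understates per-cycle percentages for TEAEs, serious TEAEs, UTIs and AESIs in the early report, and the planned tables do not allow a correction. The direction follows from the text, but the size does not.

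Under the assumptions above and a cut-off 12 to 26 weeks after the last randomisation, about 2–3%, 10–12%, 14–16% and 16–20% of Cycles 1 to 4 have under 12 weeks of follow-up. A true 12-week risk of 20% reads about 0.3 to 2 points low, generally more in later cycles and less with early onset. Whole-cycle percentages read about 3 to 8 points low, most in Cycle 2. A later cut-off shrinks the 12-week effect.

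Unequal cycle length is a separate matter. It lowers crude percentages in later cycles in the final report too. The primary efficacy analysis is not affected.

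**What to change.** In SAP 7.7.1 and 7.8, add for each Dysport Cycle:

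- (a) Subject-years at risk and exposure-adjusted first-event rates for TEAEs, serious TEAEs, UTIs and AESIs, with time stopped at the first event, next injection, last contact or cut-off. Under constant hazard these rates return the assumed hazard in every simulated cycle. If events cluster early they still depend on cycle length, so (b) is needed as well.
- (b) A table of events in the first 12 weeks of the cycle, using either a Kaplan-Meier 12-week incidence or a denominator of all subjects injected at least 12 weeks before the cut-off. Define that denominator by injection date alone. Keeping recent injections only where the subject has already withdrawn would select for withdrawals due to adverse events and push the percentage up.

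Both items also make cycles of different length easier to compare, so they are worth keeping in the final report. If the redacted trigger or the shells already contain a follow-up rule, state it in SAP 7.7.1.

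The cost is SAP wording, extra versions of the overview and SOC/PT tables, and smaller denominators in the restricted table. No new data are needed and conduct does not change.

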8 CHANGES IN PLANNED ANALYSES

Not applicable.

9 DATA ISSUES

Not applicable.

